APPENDIX E: INFORMATION REGARDING EFFECTIVENESS OF CONTRACEPTIVE METHODS

For Subjects Participating in the Study:

The following methods that can achieve a failure rate of <1% per year when used consistently and correctly are considered as highly effective birth control methods.

Such methods include:

- Combined (estrogen and progestogen containing) hormonal contraception associated with inhibition of ovulation¹
 - Oral,
 - Intravaginal, and
 - Transdermal,
 - Progestogen-only hormonal contraception associated with inhibition of ovulation,¹
 - Oral,
 - Injectable, and
 - Implantable,²
 - Intrauterine device (IUD),²
 - Intrauterine hormone-releasing system (IUS),²
 - Bilateral tubal occlusion,²
 - Vasectomized partner,^{2,3} and
 - Sexual abstinence.⁴
4. Hormonal contraception may be susceptible to interaction with the IMP, which may reduce the efficacy of the contraception method.
 5. Contraception methods that in the context of this guidance are considered to have low user dependency.
 6. Vasectomized partner is a highly effective method provided of avoiding pregnancy that partner is the sole sexual partner of the woman of child bearing potential trial participant and that the vasectomized partner has received medical assessment of the surgical success.
 7. In the context of this guidance, sexual abstinence is considered a highly effective method only if defined as refraining from heterosexual intercourse during the entire period of risk associated with the study treatments. The reliability of sexual abstinence needs to be evaluated in relation to the duration of the clinical trial and the preferred and usual lifestyle of the subject.

Source: CTFG 2014.

APPENDIX F: SCHEDULE OF EVENTS (PHASE 1 ONLY)

Study Phase	Screening	Treatment Period										Follow-up Period		
	Screening	Cycle 1			Cycle 2			Cycle 3 and Beyond ¹		EOT ²	Safety Follow-up ³	Survival Follow-up		
		Week 1	Week 2	Week 3	Week 1	Week 2	Week 3	Week 1	Week 2					
Study Day	-28 to -1	1	2	8	15	1	2	8	15	1	8	ASAP After Last Dose	30 Days After Last Dose	Every 12 Weeks
Visit Window (Days)	-	-	-	±1	±1	-	-	±1	±1	-	±1		+5	±7
Study Procedures														
Informed Consent	X													
Inclusion/Exclusion Criteria	X													
Assignment/Randomization to Treatment Arm ⁴		X												
Medical History	X													
Vital Signs, Height, Weight ⁵	X	X	X	X	X	X			X	X			X	
Physical Examination ⁶	X	X				X				X			X	
ECOG Performance Status	X	X		X	X	X			X	X			X	
Electrocardiogram ⁷	X	X			X ⁷					X			X	
Adverse Events		X	X	X	X	X	X	X	X	X	X	X	X	
Prior and Concomitant Medications and Therapies ⁸	X	X	X	X	X	X	X	X	X	X	X	X	X	
Survival and Additional Treatment Status ⁹														X
Laboratory/Sample Collection														
Virology Screen ¹⁰	X													
Urinalysis	X												X	
CD4 Count	X													
Pregnancy Test ¹¹	X	X				X				X			X	
Clinical Hematology, Serum Chemistry, Liver Function ¹²	X	X	X	X	X	X	X	X		X	X		X	
Coagulation Panel ¹³	X	X											X	
CA-125 Assessment ¹⁴	X	X				X				X		X		
Serum/Plasma for Immune Monitoring ¹⁵		X	X	X		X	X	X		X	X	X		
HLA-Typing ¹⁶	X													

Study Phase	Screening	Treatment Period										Follow-up Period				
	Screening	Cycle 1			Cycle 2			Cycle 3 and Beyond ¹		EOT ²	Safety Follow-up ³	Survival Follow-up				
		Week 1	Week 2	Week 3	Week 1	Week 2	Week 3	Week 1	Week 2							
Study Day	-28 to -1	1	2	8	15	1	2	8	15	1	8	ASAP After Last Dose	30 Days After Last Dose	Every 12 Weeks		
Visit Window (Days)	-	-	-	±1	±1	-	-	±1	±1	-	±1		+5	±7		
Endocrine Testing ¹⁷	X	X								X						
PBMC ¹⁸		X		X		X		X		X	X	X				
Serum for Epacadostat (PK) ¹⁹						X	X									
Shedding and Clearance ²⁰		X	X	X		X	X	X								
Blood sample for CRS-207 testing ²⁸												X		X		
Archived Tumor Specimen	X															
Plasma/Whole Blood for Pharmacodynamic Analysis ²¹		X	X			X	X			X		X				
Tumor Biopsy ²²	X								X							
Tumor Evaluation ²³	X	Every 9 weeks (± 7 days)											X	X ⁹		
Blood for CRS-207 Surveillance ²⁸												X		X		
Investigational Product Administration																
Administer CRS-207 ²⁴		X				X				X						
Epacadostat ²⁵		X ²⁵		← BID →												
Epacadostat Compliance & Accountability ²⁶		X	X	X	X	X	X	X	X	X	X	X	X			
Other Concomitant Medication																
Antibiotics ²⁷												X				

Footnotes

1. Treatment will continue for 6 cycles as long as there is potential for clinical benefit. After 6 cycles, treatment may continue if there is continued potential benefit and upon approval from the Study Medical Monitor. After Cycle 3 Day 8, visits between administrations of CRS-207 will be conducted based on Investigator's discretion. After Cycle 3 Day 1, initiation of a new cycle may be delayed up to 3 days due to subject scheduling. Epacadostat should continue uninterrupted during the treatment period.
2. An EOT Visit will occur as soon as determined that the subject will permanently discontinue study treatment, and at least 7 days after the last dose of CRS-207. If the EOT visit coincides with a regular study visit, the EOT evaluations will supersede those of that scheduled visit, and the data should be entered in the EOT page in the eCRF. If the EOT Visit occurs >21 days after the last administration of study drug, procedures from the EOT and Safety Follow-up visits may be collected as a single Safety Follow-up Visit.
3. A Safety Follow-up Visit will be scheduled 30 days (+5 days) post last dose of study treatment. If the subject begins another anticancer therapy before the Safety Follow-up Visit, every effort will be made to complete all of the Safety Follow-up Visit assessments prior to commencing the new therapy. If there is an adverse event in need of

monitoring beyond the Safety Follow-up Visit, the subject will be followed until resolution or confirmed stability of the adverse event. If a CT scan was collected within 9 weeks (± 7 days) of the Safety Follow-up Visit, then a CT scan at the Safety Follow-up Visit will not be mandatory.

4. For Phase 1, enrollment form will be completed and sent to Medpace for treatment assignment. As an added safety measure during Phase 1, Dose Cohort 1 will have a staggered enrollment of no more than 1 new subject treated per week during the dose escalation phase. Thereafter, a decision to further stagger combination enrollment will be made by the SRC and will be based on emergent safety data.
5. Vital sign measurements consist of seated BP, pulse, respiratory rate, and temperature. Pulse oximetry will be measured if clinically indicated. Weight will be taken on Day 1 of each cycle. Height is required at screening only.
6. Complete physical examinations will be conducted at screening and Safety Follow-up Visits; symptom-directed physical examinations will be conducted on Day 1 of all other cycles and at the EOT visit. Physical exams may be conducted up to 3 days before dosing with CRS-207.
7. 12-lead ECG assessments will be conducted on all subjects at screening, Cycle 1 (Day 1 and Day 15), and on Day 1 of every odd numbered cycle (Cycle 3, Cycle 5, etc.) while on treatment. Serial ECGs will be collected pre-dose and approximately 60 to 90 minutes after the first dose of epacadostat at Cycle 1 Day 2. For Subject receiving CRS-207 monotherapy, ECG will be collected pre-dose and approximately 60-90 minutes after their CRS-207 infusion has begun. In order not to confound interpretation of the ECG, if anti-emetics or other prophylactic agents are given then these should be given after the pre-dose ECG rather than before. ECGs will be performed with the subject in recumbent or semi-recumbent position after 5 minutes rest. Subsequent ECGs will be obtained as clinically indicated, and at the Safety Follow-up Visit.
8. All concomitant medications and cancer-related therapies and procedures will be recorded within 28 days before study treatment begins and 30 days after the last dose of study drug, or until the subject completes the Safety Follow-up Visit. In addition, all prior and post-study treatment anticancer therapy will be recorded in the eCRFs.
9. Once a subject has radiographic confirmed PD, discontinues study treatment or starts a new anticancer therapy, the subject moves into the Survival Follow-up phase. Subject will be contacted every 12 weeks (by phone/email is permissible if no recent (with 14 days) medical charting is available) to collect data on survival and any additional cancer-related therapies that may have been administered. Follow-up will continue until death, withdrawal of consent, or the end of the study, whichever occurs first.
10. Virology screen will include the following: HIV antibody, hepatitis B (HBsAg), and hepatitis C (HCV-RNA, Qualitative); additional virology may also be evaluated. Virology screen will be performed by the site's local laboratory.
11. Serum pregnancy test is required for women of childbearing potential only and must be performed and confirmed negative prior to the first dose of study treatment. Urine pregnancy test for women of childbearing potential should be repeated and confirmed negative on Day 1 of each cycle and at the Safety Follow-up Visit. Serum testing may be conducted if urine pregnancy testing is unavailable. Serum and/or urine pregnancy test may be conducted up to 3 days before dosing with CRS-207. Pregnancy testing will be performed by the site's local laboratory.
12. Refer to [Appendix A](#) for complete list of clinical hematology, chemistry and liver function analytes. Day 1 blood draws may be taken up to 3 days before dosing with CRS-207. Blood draws required on Day 2 after CRS-207 dosing for Cycle 1 and Cycle 2; additional timepoints may be obtained if clinically indicated. For subject in Arm 3 at Cycle 3, chemistry, hematology and liver function should be collected on Day 2 after their first infusion of CRS-207. **To avoid inadvertent contamination of a central line (eg, infusion ports, PICC lines), blood draws MUST NOT be collected from a central line for at least 4 days after infusion of CRS-207 has started.** If LFTs are found to be abnormal ($>$ Grade 2), frequency of monitoring should be increased to once per week until LFTs have resolved to baseline at which time chemistry test monitoring will be performed according to institutional standards or approximately weekly, whichever is shorter. Liver function does not need to be monitored once per week indefinitely for persistent low-grade abnormalities. Appropriate liver function monitoring intervals should be discussed with the Study Medical Monitor. Hematology, chemistry and liver panel will be performed by the site's local laboratory.
13. Coagulation panel will include the following: D-dimer, fibrinogen, INR of PT, and aPTT; INR should be monitored weekly for the first 4 weeks after initiation of coumarin-based anticoagulants (see [Section 5.6.2](#) for anticoagulant restrictions) and upon discontinuation of epacadostat. Coagulation testing will be performed by the site's local laboratory.
14. CA-125 will be assessed at screening as close to but no more than 14 days before the first study treatment, then on Day 1 of each cycle while on treatment (or every 3 weeks if subject dosing is delayed). Subjects who discontinue treatment for reasons other than PD should continue to have CA-125 assessed every 9 weeks until the start of a new anticancer therapy, documented PD, death, or the end of the study, whichever occurs first. Additional CA-125 timepoints collected per institutional standard should also be entered into the eCRF. Subjects considered CA-125 evaluable should have CA-125 repeated no earlier than 28 days if a CA-125 is reduced by 50% from baseline. See section [Appendix C](#) for more details.
15. Approximately 7.5 mL of whole blood for immune monitoring will be drawn as indicated. After Cycle 3, serum and plasma for immune response analysis will be collected at odd numbered Cycles (eg, Cycle 5, Cycle 7, etc.) Plasma will not be collected for Day 8 time points. Samples will be sent to the central laboratory.
16. The HLA-typing should include type A and B of class I antigens, low resolution. HLA will be performed by the site's local laboratory.

17. Endocrine testing will include: adrenocorticotrophic hormone, serum cortisol (9 AM), luteinizing hormone prolactin, thyroid stimulating hormone, free thyroxine (T4), total triiodothyronine (T3). After Cycle 3, endocrine testing will be completed every 12 weeks (at Cycle 7, Cycle 11, etc.) Endocrine testing will not be collected for CRS-207 monotherapy dosed subjects.
18. Approximately 70 mL of whole blood to be processed as described in the Laboratory Manual. After Cycle 3, PBMCs will be collected on Day 1 for odd numbered Cycles only (eg, Cycle 5, Cycle 7, etc.).
19. Serum PK sample (3.5 mL) for epacadostat will be taken on Cycle 2 Day 1 at pre-dose, 2 (+/- 5 minutes), 4 (+/-10 minutes), and 6 (+/-15 minutes) hours after the morning dose of epacadostat. A pre-dose PK sample will be collected on Cycle 2 Day 2. Samples will be sent to the Central Laboratory. Epacadostat will be administered in clinic on Cycle 2 Day 1 and Day 2 in order to collect pre-dose blood sample for PK. PK samples will not be collected for those on CRS-207 monotherapy .
20. In Phase 1 US sites only: urine, rectal swab, oral swab, and whole blood will be collected from subjects treated with CRS-207 pre-dose, and at 6 hours, 18 to 24 hours, and Day 8 post-infusion on Cycle 1 and Cycle 2. **DO NOT use the central line for blood sample collection.** Additional assessments will be performed if results are positive for CRS-207 at the Day 8 time point. Samples will be sent to the central laboratory.
21. Plasma and whole blood (7 mL) for pharmacodynamic analysis will be collected only for those who receive epacadostat) at the following timepoints: Cycle 1 Day 1 and Cycle 2 Day 1 pre-dose, 2, and 6 hours post-dose; Cycle 1 Day 2 and Cycle 2 Day 2 prior to epacadostat dose; and Cycle 3 Day 1 and every odd numbered Cycle Day 1 thereafter) prior to epacadostat dose.
22. Paired tumor biopsies collected during the screening period (pre-dose) and on Cycle 2 Day 15 (+7 days). Paired biopsies are mandatory during Phase 1. Fine needle aspiration will not be acceptable. Samples will be sent to the Central Laboratory.
23. Tumor evaluations will be performed using CT with contrast of the abdomen and pelvis (or MRI in case of contrast dye allergy) within 28 days prior to treatment, and repeated every 9 weeks (± 7 days) after initiation of study drug using the same assessment technique. Subjects who discontinue treatment for reasons other than PD should continue to have their disease assessed by CT every 9 weeks (± 7 days) until the start of a new anticancer therapy, documented PD, death, withdrawal of consent, or the end of study, whichever occurs first. Data from any standard of care CT scans may also be collected for tumor evaluation.
24. CRS-207 will be administered on Day 1 of each cycle via IV infusion over approximately 1 hour. Before each CRS-207 infusion, subjects will be pre-medicated with acetaminophen and saline will be given immediately before and after infusion with CRS-207 (Section 5.5.2.1). Vital signs (BP, pulse, respiratory rate, temperature) will be obtained every 30 minutes (+/- 5 minutes) during CRS-207 infusion and every hour (+/- 5 minutes) during post-infusion follow-up. Subjects will be observed for at least 4 hours after each infusion. Subjects who are not stable enough to be released at 4 hours after infusion should continue to be monitored until stable. Presence of fever alone does not indicate subject is not clinically stable. Document the time subject becomes stable in the medical records. **To avoid inadvertent contamination of a central line (eg, infusion ports, PICC lines), DO NOT administer CRS-207 or saline through a central line during infusion or for 4 days following infusion. DO NOT flush the central line for any reason during and for 4 days after CRS-207 infusion.**
25. Enough epacadostat will be dispensed to last one cycle. Phase Arm 1: Epacadostat will be administered orally starting on Day 2 and BID thereafter. Tablets will be taken at the assigned dose in the morning and evening, approximately 12 hours apart. Epacadostat will be administered in clinic on Cycle 2 Day 1 and Day 2 in order to collect pre-dose blood sample for PK. Epacadostat dosing does not apply to CRS-207 monotherapy (Phase 1, Arm 2).
26. At each visit, provide a dosing diary and instructions on recording each dose of epacadostat. Collect unused epacadostat and review completed dosing diary with subject at following visit.
27. A 7-day course of antibiotics will be administered at the EOT visit after blood has been collected for CRS-207 culture to ensure clearance of CRS-207. Antibiotic regimen must be completed prior to initiation of any other cancer-related therapy. Subjects with a central line port will receive 1 dose of IV antibiotics followed by 6 days of oral antibiotics; all other subjects will receive 7 days of oral antibiotics (refer to Section 5.6.3). Site personal will contact the subject by to confirm compliance with the antibiotic treatment and document in source and CRFs.
28. At EOT, blood for culture will be collected prior to initiation of antibiotics (if applicable, blood must also be collected through the central line port) to assess CRS-207 clearance. After EOT, blood for culture will be collected for CRS-207 surveillance at [REDACTED]

aPTT = activated partial thromboplastin time; ASAP = as soon as possible; BID = twice daily; BP = blood pressure; CA-125 = cancer antigen 125; CT = computed tomography; ECG = electrocardiogram; ECOG = Eastern Cooperative Oncology Group; eCRF = electronic case report form; EOT = End-of-Treatment; HIV = human immunodeficiency virus; HLA = human leukocyte antigen; INR = international normalized ratio; IRT = Interactive Response Technology; IV = intravenous; LFT = liver function test; MRI = magnetic resonance imaging; PBMC = peripheral blood mononuclear cells; PD = disease progression; PICC = peripherally inserted central catheter; PK = pharmacokinetic; PT = prothrombin; SRC = Safety Review Committee.

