CRS-207, live, attenuated, double-deleted *Listeria monocytogenes* encoding human mesothelin (*Lm ΔactA/ΔinlB* hMeso), is formulated as 1×10^9 CFU suspended in [REDACTED], filled into a single-use 2-mL glass vial with a gray butyl stopper and aluminum crimp seal with a flip off cap. 1.0 mL CRS-207 is diluted in sterile saline prior to IV infusion.

Epacadostat, an indoleamine 2,3-dioxygenase (IDO) 1 inhibitor, is available as 25 mg and 100 mg tablets packaged in high-density polyethylene bottles. Epacadostat will be dispensed for 3-week cycles for the duration of the study. Tablets are taken at the assigned dose BID in the morning and evening, approximately 12 hours apart.

Pembrolizumab, Pembrolizumab can be in liquid or lyophilized powder format in single-use vials. Refer to the package insert for dose preparation instructions.

ADU-CL-11 Treatment Cycles by Arm

Phase	Arm	Dose ¹ / Route	Treatment Cycle
1	CRS-207/ IDO	CRS-207: 1×10^9 CFU by IV infusion over ~ 1 hour IDO: 100 mg or 300 mg BID Oral	CRS-207: Day 1 of each cycle (Cycles 1-6); Q6W thereafter IDO: BID starting Cycle 1 Day 2
	CRS-207	CRS-207: 1×10^9 CFU by IV infusion over ~ 1 hour	CRS-207: Day 1 of each cycle (Cycles 1-6); Q6W thereafter
2	CRS-207/ Pembro/ IDO	Pembro: 200 mg by IV infusion over 30 min CRS-207: 1×10^9 CFU by IV infusion over ~ 1 hour IDO: 300 mg Oral BID ¹	Pembro: Day 1 of each cycle CRS-207: Day 2 of each cycle (Cycles 1-6); Q6W thereafter IDO: BID starting Cycle 1 Day 3
	CRS-207/ Pembro	Pembro: 200 mg by IV infusion over 30 min CRS-207: 1×10^9 CFU by IV infusion over ~ 1 hour	Pembro: Day 1 of each cycle CRS-207: Day 2 of each cycle (Cycles 1-6); Q6W thereafter
BID = twice daily; CFU = colony-forming units; IDO = epacadostat; IV = intravenous; pembro = pembrolizumab; Q6W = once every 6 weeks ¹ RP2D of epacadostat based on Phase 1 dose-evaluation parameters and determined by the SRC; the phase 2 dose may be further adjusted during Phase 2 Safety Run-in			

DOSE-LIMITING TOXICITY:

During Phase 1, the DLT evaluation period is defined as Cycle 1 (21 days).

During the Phase 2 Safety Run-in, the DLT evaluation period is defined as Cycle 1 (the first 21 days).

Non-Hematologic Events

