23. **CRS-207:** will be administered on Day 2 of each cycle via IV infusion over approximately 1 hour (no in-line IV filter should be used). After Cycle 6, CRS-207 will be administered every six weeks, at even numbered visits (Cycle 8, Cycle 10, etc.) Study Medical Monitor must be notified for dose delays as noted in Section 4.3.1. Before each CRS-207 infusion, subjects will be pre-medicated with acetaminophen and saline will be given immediately before and after infusion with CRS-207 ([Section 5.5.2.1](#)). Subjects will be observed for at least 4 hours after each infusion. Subjects who are not stable enough to be released at 4 hours after infusion should continue to be monitored until stable. Presence of fever alone does not indicate subject is not clinically stable. Document the time subject becomes stable in the medical records. **To avoid inadvertent contamination of a central line (e.g. infusion ports, PICC lines), DO NOT administer CRS-207 or saline through a central line during infusion or for 4 days following infusion. DO NOT flush the central line for any reason during and for 4 days after CRS-207 infusion.**
24. **Epacadostat:** Epacadostat will be administered orally starting on Day 3 and BID thereafter. Tablets will be taken at the assigned dose in the morning and evening, approximately 12 hours apart. Epacadostat will be administered in clinic on Cycle 2 Day 1 and Day 2 in order to collect pre-dose blood sample for PK. Epacadostat dosing does not apply to CRS-207/pembro arm.
25. **Epacadostat Diary:** At each visit, provide a dosing diary and instructions on recording each dose of epacadostat. Collect unused epacadostat and review completed dosing diary with subject at following visit.
26. **Antibiotics:** A 7-day course of antibiotics will be administered at the EOT visit AFTER blood has been collected for CRS-207 culture to ensure clearance of CRS-207. Antibiotic regimen must be completed prior to initiation of any other cancer-related therapy. Subjects with a central line port will receive 1 dose of IV antibiotics followed by 6 days of oral antibiotics; all other subjects will receive 7 days of oral antibiotics (refer to [Section 5.6.3](#)). Site personal will contact the subject by to confirm compliance with the antibiotic treatment and document in source and CRFs.
27. **Pembrolizumab:** will be administered on Day 1 of each cycle via IV infusion over 30 minutes (-5/+10 minutes).

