1.3.1 CRS-207

The proposed dose level for this study (1×10^9 CFU) is the MTD as determined in the Phase 1 solid tumor dose escalation study (Protocol VAC07001), which included 2 ovarian cancer patients. It is also the dose administered in ongoing studies in other oncologic indications, which are demonstrating further safety and tolerance of this dose.

Treatment emergent adverse events (TEAEs) temporally related to CRS-207 administration which are common and may vary in degree of severity include fevers, chills, nausea, vomiting, fatigue, headache and changes in blood pressure; generally, these were reported as immediate, transient, and mild and resolve within 48 hours following CRS-207 infusion. Changes in hepatic enzyme levels and hematological parameters (lymphopenia) are also anticipated to varying degrees of severity. These effects are likely a consequence of the mechanism of action of CRS-207 through the activation of the innate immune system and release of proinflammatory cytokines and chemokines. Some of these infusion-related events may be mitigated by pre-medication with acetaminophen and administration of saline prior to and following CRS-207 infusion. Based on available results from clinical studies, continued clinical development of CRS-207 is warranted.

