3 STUDY DESIGN

The study is designed to assess the safety and efficacy of the following investigational treatment regimens in adult females with epithelial ovarian, fallopian, or primary peritoneal cancer that is platinum-resistant (i.e. has progressed within 6 months after completing platinum-based chemotherapy):

- CRS-207/epacadostat/pembrolizumab (CRS-207/IDO/pembro)
- CRS-207/pembrolizumab (CRS-207/pembro)

The study will be conducted in 2 phases as depicted in the study schematic (Figure 1). Phase 1 seeks to evaluate safety and tolerability and is aimed at determining the recommended Phase 2 dose (RP2D) of epacadostat administered with CRS-207 for further evaluation in Phase 2. The randomized Phase 2 portion of the study will begin with a safety-run in to evaluate the addition of pembrolizumab, followed by a 2-stage design to evaluate safety and efficacy in subjects who have received no more than 3 prior chemotherapy regimens for locally advanced or metastatic disease.

Figure 1 Study Schematic

The Schedules of Events for Phases 1 and 2 are provided in [Appendix F](#) and [Table 1](#), respectively. The study consists of a 28-day screening period, followed by administration of study drug(s) in 3-week cycles. Treatment will continue for as long as there is adequate safety and potential for clinical benefit with the exception that pembrolizumab may be given for up to 24 months to subjects without disease progression. After 6 cycles, CRS-207 will be administered every 6 weeks (Q6W); all other assigned treatments remain the same.

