6.8. Study Drug Exposure and Compliance

The number of cycles of administration (of any dose amount) of pembrolizumab and epacadostat will be reported as a continuous and categorical outcome; categories for reporting will include: < 5 Cycles; 5 - 15 Cycles; > 15 to 25 Cycles; and > 25 Cycles.

The number of infusions of CRS-207 will also be reported as both a continuous and categorical outcome; categories for reporting will be < 5 infusions; 5 – 10 infusions; > 10 to 15 infusions; and > 15 infusions.

For CRS-207, the average volume administered for each infusion (or cycle) will be summarized by therapy. This will be calculated for each subject in (mL / infusion or mL / Cycle):

$(\text{Sum of Total Volume Administered [mL]}) / (\text{Total Number of Administrations})$

The average dose intensity for each pembrolizumab cycle will be summarized. This will be calculated for each subject in (mg / Cycle):

$(\text{Sum of Total Dose Received [mg]}) / (\text{Total Number of Administrations})$

Sponsor: Aduro Biotech, Inc.
Protocol Number: ADU-CL-11
Version and Date: Version 1.0, 03MAY2018

The incidence of infusion interruptions, as well as the total number of interruptions will be displayed for CRS-207 and pembrolizumab separately. Reasons for infusion interruption will also be summarized.

The incidence and number of epacadostat dose reductions will be summarized.

For epacadostat, the mean daily dose will be summarized. This will be calculated for each subject in (mg / Day):

(Sum of Total Doses Received [mg]) / (Duration of epacadostat therapy)

Duration of treatment for each drug, based on similar definitions provided in 5.3, will also be summarized.

Epacadostat dosing, CRS-207 and pembrolizumab administrations, infusion interruptions, and dose reduction information, as well as derived drug exposure metrics, will be listed.

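### The Phase 1 schedule in Appendix F keeps CRS-207 at every 3 weeks after Cycle 6, where the rest of the protocol and the SAP move it to every 6 weeks

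*Protocol*

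**What the plan says.** **Appendix F (Phase 1 Schedule of Events).** Footnote 24 states: "CRS-207 will be administered on Day 1 of each cycle via IV infusion over approximately 1 hour". The grid row labelled "Administer CRS-207" is marked on Day 1 of Cycle 1, of Cycle 2, and of the single column that covers Cycle 3 and everything later. Footnote 1 deals with treatment past Cycle 6: "After 6 cycles, treatment may continue if there is continued potential benefit and upon approval from the Study Medical Monitor". It says nothing about the CRS-207 interval, and no other Appendix F footnote mentions a 6-week interval.

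**Elsewhere.** The synopsis treatment table and Section 5.1, Table 5 give, for both Phase 1 arms, "CRS-207: Day 1 of each cycle (Cycles 1-6); Q6W thereafter". SAP Section 5.1, Table 3 gives the same entry. The synopsis design text, protocol Section 3 and SAP Section 3.1 say in prose that CRS-207 moves to 6-weekly dosing after six cycles.

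**Phase 2 schedule.** Table 1, footnote 23 does carry the switch: "After Cycle 6, CRS-207 will be administered every six weeks, at even numbered visits (Cycle 8, Cycle 10, etc".

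**The concern.** A schedule of events is what site staff work from visit by visit. Where it gives a dosing frequency, in a grid row and again in a footnote, staff may follow it without going back to Table 5. Appendix F uses its footnotes to reduce other activities over time: ECGs, immune monitoring, endocrine tests and PBMC collection all have a later frequency written out. A reader would expect a change in CRS-207 frequency to be written out in the same way, and the Phase 2 schedule does so.

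At stake is the dosing of Phase 1 subjects who stay on treatment beyond Cycle 6. CRS-207 is a live attenuated bacterium, and each infusion brings saline, hours of observation and the fevers and rigors that Section 5.5.2.1 tells sites to expect. There is also a record-keeping question. SAP Section 6.3 lists improperly administered doses among possible major deviations. A Cycle 7 infusion in Phase 1 would comply with Appendix F and depart from Table 5.

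**Working it through.** The plan gives no infusion count to reproduce, so the check is a comparison of texts followed by a simple count.

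**Side by side, CRS-207 in Phase 1 after Cycle 6**

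| Place | Interval after Cycle 6 |
|---|---|
| Appendix F, CRS-207 row | every cycle (3 weeks), no end point |
| Appendix F, footnote 24 | every cycle (3 weeks), no end point |
| Appendix F, footnote 1 | continuation allowed with approval; interval not addressed |
| Synopsis text and treatment table | 6 weeks |
| Section 3 | 6 weeks |
| Section 5.1, Table 5 | 6 weeks |
| SAP Section 3.1 and Table 3 | 6 weeks |

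The conflicting footnote is prose, so the finding does not depend on how the grid was extracted from PDF.

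**Inputs for the count.** Cycle length is 3 weeks (Section 3). Both schedules give one infusion per cycle through Cycle 6. Assumption: the first 6-weekly dose falls 6 weeks after Cycle 6 Day 1, at Cycle 8, as Table 1 footnote 23 has it for Phase 2. The Phase 1 text does not name the cycles.

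**Formulas.** Cumulative infusions by Cycle n, for n of 6 or more:

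- Appendix F: n
- Table 5: 6 + floor((n − 6)/2)

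| By Cycle | Appendix F | Table 5 | Excess |
|---|---|---|---|
| 6 | 6 | 6 + 0 = 6 | 0 |
| 8 | 8 | 6 + 1 = 7 | 1 |
| 10 | 10 | 6 + 2 = 8 | 2 |
| 12 | 12 | 6 + 3 = 9 | 3 |

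Cycle 12 Day 1 falls 3 × 11 = 33 weeks after the first dose. The ratio there is 12/9 = 1.33, or 33% more infusions. After Cycle 6 the dosing rate is 6/3 = 2 times the intended one.

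**Sensitivity to the assumption.** If the 6-weekly doses fell at Cycles 7, 9 and 11 instead, the Table 5 count by Cycle 12 would still be 6 + 3 = 9. The counts at Cycles 8 and 10 would also be unchanged, at 7 and 8.

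**The case against.** The strongest reply is that the rule is clear where dosing is defined. Section 5.1 sends the reader to Table 5. Section 3 points to Appendix F and states the 6-weekly rule in the same paragraph. Section 6 ties the Schedule of Events to study assessments rather than to dosing. On this view Appendix F has only left out a qualifier. In addition, footnote 1 requires Study Medical Monitor approval before a Phase 1 subject continues past Cycle 6, which gives someone on the sponsor's side a chance to catch the error. Both arguments stand as mitigation: the intended regimen is not in doubt, and the route to harm has a checkpoint. They do not remove the conflict, because footnote 24 is a dosing instruction that, read literally, is a different regimen.

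Some stronger readings are tempting, and the documents do not support them.

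- *That 3-weekly dosing after Cycle 6 is shown to be unsafe.* Section 1.3.1 says the dose level "is the MTD as determined in the Phase 1 solid tumor dose escalation study", but the same dose is planned every 3 weeks for the first six cycles. No document says that continuing at that interval is unsafe.
- *That SAP exposure categories would be wrong.* SAP Section 6.8 says "The number of infusions of CRS-207 will also be reported as both a continuous and categorical outcome". It counts infusions given, so a subject with 12 infusions would be classified correctly.
- *That required ECGs are missing.* The extracted grids show no ECG mark on the day of the first epacadostat dose (Cycle 1 Day 2 in Appendix F, Cycle 1 Day 3 in Table 1). Footnote 7 of each schedule already requires those ECGs, so marking the cells is optional tidying. Other apparent ECG blanks, in Cycle 6 of Table 1, lie in columns where the extraction is unreliable, and nothing should rest on them.
- *That Table 1 has the same fault, because it marks CRS-207 in odd cycles from Cycle 5 on.* Footnote 23 already limits later doses to even-numbered cycles.

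**Conclusion.** The inconsistency is real and minor. Appendix F, in both its CRS-207 row and footnote 24, contradicts every other statement of the Phase 1 CRS-207 schedule. Followed literally, it doubles the infusion rate after Cycle 6 and gives 3 extra infusions by Cycle 12 (12 instead of 9), under the assumption about dosing cycles stated above.

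It reaches only Phase 1 subjects who continued past Cycle 6. Their number is not given and may be zero. SAP Section 3.5 mentions 2 subjects with the option to continue treatment but does not say which phase they were in. The dose-limiting toxicity window is Cycle 1, so DLT counts and the choice of the Phase 2 dose are untouched, as are the Phase 2 stage rules, sample size and error rates. Section 3.5 also records that development of CRS-207 was stopped in December 2017. The practical value of the correction is therefore mostly in classifying deviations consistently and in any reuse of the schedule.

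**What to change.** In Appendix F, limit footnote 24 to Cycles 1 to 6 and add the 6-weekly interval after that, using the Table 5 entry. Name the cycles (8, 10 and so on), as Table 1 footnote 23 does. Annotate the CRS-207 row in the column for Cycle 3 and later in the same way.

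The cost is one phrase in a footnote and one grid annotation. It adds no visits, procedures or analyses. If subjects did continue past Cycle 6 in Phase 1, state in the deviation review that Table 5 is the reference schedule, so that 3-weekly infusions after Cycle 6 are all handled in one way.
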